4.3 Study Enrollment Procedures

All patients will be referred from primary care physicians, cardiologists, and neurologists to neurosurgeons, vascular surgeons, and cardiologists. We will enroll patients after they consult their respective surgical team, who will be providing their care and a decision has been made to proceed with a CEA. We will not be part of that decision-making process. Patients will be approached after giving permission to discuss the study with the research team and after the study team confirms that the potential subjects are able to provide informed consent. The potential participants are then informed about the study by either a study coordinator or physician, given

opportunity to ask questions, are offered participation, and if they agree, subsequently provide informed consent to participate in the study. All participants who consent will be given a copy of the informed consent form for their records and the original consent form will be filed in their study subject binder.

Typically, the study procedures post-consent will be conducted at the site; however, if necessary and at sites where home visits are permissible, the study visit and procedures can be conducted at the subject's home. If the home study visit includes a blood draw, these will be conducted by study personnel authorized to draw blood (e.g. physicians, nurse, phlebotomist, coordinators with phlebotomy training). The blood samples drawn for the study will be delivered to the study's corresponding laboratories ambiently (site's clinical laboratory for the CK, CBC with differential, lipid panel, CMP, ESR, C-RP and if the ApoE sample is also drawn during that home visit, then it will be hand delivered by CUMC study staff or shipped to CUMC-IGM Biobanking Core by the other sites as usual). The team will use appropriate safety equipment for the draw, disposal of equipment (sharp's container), and transport the blood sample in IATA approved Category B Ambient Shipping boxes, via private vehicles, until they are ready to be delivered to the site's clinical laboratory and/or ready to be shipped/delivered to CUMC-IGM Biobanking Core.

All potential subjects identified will be screened for eligibility and reasons for ineligibility or nonparticipation of eligible candidates will be documented in the Study Screening Log (see Appendix III). The Study Screening Log will be collected on a monthly basis from all sites documenting all subjects considered for participation in the study.

After consent, the participants will be screened for MCI. If they pass the screening tests, they will be randomized by the coordinator on a central, web-based system created and maintained by the Statistical Analysis Center (SAC) at the Mailman School of Public Health at Columbia University and considered enrolled. The randomization will be based on each patient's pre-existing statin regimen, each patient will be grouped into one of the three previously described arms after the screening process. The randomization design will be stratified by center, previous use of statin and in random blocks of 4 and 6.

4.3.1 Gender and Minority Issues.

Although we do not select patients on the basis of gender or race, we will make every effort to facilitate minority recruitment.

We think that at least 50% of the patients will be female, in line with the gender difference in prevalence of carotid artery stenosis. As per previous studies, the projected gender and ethnic distribution is 50% female, 80-85% white, 5% African American, 5% Hispanic/Latino, and 5% Asian/Pacific Islander/other. It must be noted that extra-cranial carotid disease tends to predominate in whites compared to other race-ethnic groups, in whom intracranial atherosclerosis is more common.

We anticipate that as a result of expanding to a multi-center trial, we will have more minority patients. Consequently, we will strive to provide a bilingual neurocognitive tester for our Spanishspeaking patients.

5 STUDY INTERVENTIONS

5.1 Interventions, Administration, and Duration

The study assigned statin dosing will be taken daily for no fewer than 2 and no greater than 18 doses prior to the participant's CEA. If the encounter and enrollment happen prior to the 18 day timepoint and the patient cannot return to the study site prior to their CEA, then the subject will be given the study drug and begin taking it no greater than 18 days prior to their CEA. We will strive to enroll the subjects as early as possible so that they may receive as many doses (up to 18 doses) prior to CEA. The date of drug start will be noted in the Medication Compliance form (diary) and the eCRF upon enrollment. The safety follow-up phone calls will begin based on when the study drug is scheduled to start or upon enrollment for Arm 1. All of the participants in each arm will be provided with instructions in the Study Medication Compliance form where they will note each dose taken or the reason(s) for missing a dose. This includes logging in their current statin use for the observational/ maximal dose group (Arm 1) and the sub-maximal dose group (Arm 2). This form will be collected when the subject returns to the medical center for their CEA. The treatment arms are as follows:

ARM 1: Subjects already on **maximal daily doses** will continue to take their daily statin during the dosing period prior to CEA (atorvastatin 80 mg, simvastatin 40 mg with/without amlodipine or simvastatin 20 mg plus amlodipine, or rosuvastatin 20 mg). No additional drug will be dispensed to this group.

ARM 2: Subjects on **sub-maximal daily doses** (atorvastatin <80 mg or simvastatin <40 mg without amlodipine and <20 mg on amlodipine or rosuvastatin <20 mg) will continue to take their daily statin during the dosing period prior to CEA PLUS they will be given the corresponding study drug bottles of:

- **Atorvastatin vs Placebo (each active study capsule = 10 mg)**

- 126 capsule count bottle
 - Coordinator will write on the label how many capsules the participants need to take when they take their statin drug each day (example: If subject is currently on 10 mg of atorvastatin, then they will need to add 7 capsules/day to potentially reach 80 mg of active drug.)

- **Simvastatin vs Placebo (each study capsule = 5 mg)**

- 126 capsule count bottle
 - Coordinator will write on the label how many capsules they need to take when they take their statin drug each day (example: If subject is

on 5 mg of Simvastatin, then they will need to add 7 capsules/day to potentially reach 40 mg of active drug unless they are also on amlodipine and then they will only potentially be optimized to 20 mg for safety.)

- **Rosuvastatin vs Placebo (each study capsule = 5 mg)**

- 54 capsule count bottle
 - Coordinator will write on the label how many capsules they need to take when they take their statin drug each day (example: If subject is on 5 mg of rosuvastatin, then they will need to add 3 capsules/day to potentially reach 20 mg of active drug)

ARM 3: Subjects that are statin naïve (no statins in the past 30 days) will be randomized to receive either 10 mg or 80 mg of atorvastatin during the dosing period.

- 18 capsule count bottle
- Subjects will take 1 (one) capsule/day

Patients who will be treated with invasive transcarotid artery revascularization (TCAR) procedures that use a special transcarotid neuro-protection system (NPS) will be excluded.

5.2 Handling of Study Interventions

Atorvastatin, simvastatin and rosuvastatin will be purchased and distributed to all the study sites through a private vendor, the Biomedical Research Institute of New Mexico (BRINM). BRINM is affiliated with the VA Cooperative Studies Program Clinical Research Pharmacy Center, and will provide the same pharmacy supply services previously managed by Columbia University's Research Pharmacy Department. For this blinded phase 3 study, drug or placebo will be provided in randomized, prepackaged bottles and shipped to all sites by BRINM.

The study drug will consist of the corresponding statin tablets over-encapsulated and back-filled with microcrystalline cellulose. The matching placebo capsules will be prepared using microcrystalline cellulose as the fill. Each dose will be self-administered daily prior to the participant's CEA. Doses will be prepared using capsule shells of the same capsule size and color within each dosing arm. The capsule sizes will be kept as small as possible in ARM 2 as they may have to take up to 7 capsules per day if they are on the lowest dose of atorvastatin or simvastatin upon randomization. For statin naïve participants in ARM 3, the capsule size for the group will be the same for both the 10 mg and the 80 mg dose per day. In ARM 3, the capsules will be larger in both arm options to accommodate the larger 80 mg pill inside the capsule. This group will only take 1 capsule per day and having the larger, but same size capsule between both options in this arm will maintain the blind.

Each bottle will be labeled with a blinded, study bottle number, dosing instruction, and other study specific information. The name of the participant and number of capsules to take per day will be written on the label by the study personnel.

BRINM will process the study medication in compliance with Certified Good Manufacturing Practices (cGMP), inspect the shipments, assign unique tracking ID number to each lot received/study drug bottles, store the medication in controlled (15°C – 30°C) limited access areas. Any temperature excursions will be communicated to the Central Coordinating Center at CUMC within one business day.

Investigators will not be involved in preparation or delivery of drug to maintain the blind. BRINM has prepared blinded and randomized drug supplies for several randomized trials. It will provide all pharmacy support for the study, including preparation of the randomization schedule, placebo and active statin drug supplies, monitoring of procedures for shipping drug to multiple sites, and documentation of drug handling and disposal of remaining study drug at its site.

Inventory will be monitored by BRINM to make sure that we maintain at least 3 bottles for each randomization option for any potential enrollment of subjects in ARM 2 and ARM 3. This will allow adequate inventory at each site for any potential randomization. Consequently, we will strive to maintain 24 bottles of study drug at each site [ARM 2 requires 6 study bottles for the atorvastatin group (3 placebo + 3 active drug for maximization); 6 study bottles for the simvastatin group (3 placebo + 3 active drug for maximization), and 6 study bottles for the rosuvastatin group (3 placebo + 3 active drug for maximization) while ARM 3 will require 3 bottles of 10 mg atorvastatin and 3 bottles of 80 mg atorvastatin.] Upon randomization of each subject, the study database will automatically send an email to BRINM to inform them of the bottle number used and the study option that needs to be replenished.

The study drug will be requested from the site's research pharmacy with a doctor's order, copy of 1st and signature page of the consent form, copy of the randomization page from the study website, site approved cover fax form, and in accordance with regulatory and pharmacy procedures. Study treatment is to be dispensed only to subjects enrolled in this study. Study treatment must be dispensed only by a pharmacist or appropriately qualified staff. Once study treatment is dispensed to a subject, it cannot be used for another. Study treatment bottles are only for the dosing period prior to CEA. None of the remaining capsules from one subject can be used for another subject.

The study pharmacist/investigator(s) must maintain accurate records demonstrating dates and amount of study drug received, to whom dispensed (subject-by-subject accounting), and accounts for any study drug accidentally or deliberately destroyed. At the end of the study, reconciliation must be made between the amount of study treatment supplied, dispensed, and subsequently destroyed at the site as per the pharmacy's destruction protocol. A written explanation is required for any discrepancies (Appendix IV).

No one will have access to unblinded treatment information on a regular basis other than the packaging pharmacy. All handling of study medication will take place using blinded bottle codes. It is not expected that serious adverse events will require revelation of treatment assignment, but the study web site will provide for online unblinding in emergencies. Revelation of treatment assignment will be available only to authorized users, who will be required to provide a clinical justification for unblinding. Each case of unblinding will be addressed by study personnel to

ensure access to unblinded treatment assignment information is limited, and that such incidents are limited to circumstances where it is necessary for the health of the patient.

5.3 Concomitant Interventions

A concomitant therapy is any drug or substance administered between time of informed consent to enroll and completion of assessments at Day 365 +/- 30 days post-CEA. The use of concomitant therapies or procedures must be recorded on the subject's Concomitant Medications and Adverse Events eCRFs, according to instructions for completion and data entry. All AEs following the administration of these therapies or procedures must be documented on the appropriate worksheet/eCRF, regardless of relatedness.

5.3.1 Allowed Interventions

Concomitant therapy with any of the following is allowed as long as the exclusion criteria described in Section 4.2 are observed:

- Medications necessary for treatment of AEs according to the discretion of the Investigator.
- Medications used in standard of care to treat CEA patients, cardiovascular risk factors, or other comorbid conditions.

5.3.2 Required Interventions

- The subjects must undergo their scheduled CEA in order to be eligible.

5.3.3 Prohibited Interventions

- During the dosing period, the subjects should not switch to other statins.
- Concomitant therapy with any investigational product is not allowed.
- Subjects will be screened for and asked not to concurrently take the following medications during the study dosing period prior to CEA:
 - *Cyclosporine;
 - *HIV Protease Inhibitors/Antivirals (e.g. roatanavir or plus roatanavir, tipranavir, lopinavir, boceprevir, saquinavir, darunavir, fosamprenavir, nelfinavir, efavirenz/tenofobir, atazanavir, simeprevir); *Hep C Protease Inhibitor/Antivirals (e.g. telaprevir);
 - *Antibiotics (i.e. cobicistat-containing products like Tybost, rifampin/rifampicin, clarithromycin, telithromycin, erythromycin);
 - *Anti-fungals (i.e. itraconazole, ketoconazole, posaconazole, voriconazole, fluconazole);
 - *Gemfibrozil; Other Fenofibrates (e.g. Tricor, fibric acid);
 - *Niacin > 1g/day or statins in combination with niacin (e.g. Vytorin, Simcor); *Colchicine;
 - *Danazol;

- *Calcium Channel Blockers: Diltiazem, Varapamil;
- * Dronedarone;
- *Amiodarone;
- *Digoxin;
- *Ranolazine;
- *Nefazodone;
- *Warfarin/Coumadin;
- *Lomitapide;
- *Grapefruit juice (subject must be willing to avoid grapefruit juice)

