2.2.1 Hypothesis

While there are several non-modifiable risk factors for eCD after CEA identified from previous research, including medically treated diabetes mellitus and the presence of the ApoE-ε4 genotype, we have only been able to identify one potentially neuroprotective factor, namely preoperative statin use. Consequently, we hypothesize that in CEA patients:

- 1) A pre-operative statin regimen is protective against eCD (12-25h) and dCD (30d); consequently, early (365d) mortality.
- 2) Maximal doses may be essential in achieving optimal neuroprotection against eCD and dCD, with lipophilic statins or those that pass the blood-brain barrier more easily achieve similar effects at lower doses.

3 **STUDY DESIGN**

[figure not shown]
This is a Phase 3, multicenter, observational (ARM 1), randomized and double-blind study (ARM 2 and ARM 3), and placebo-controlled (ARM 2), where 1,000 carotid stenosis outpatient participants will be assigned to a specific daily statin regimen of no fewer than 2 and no greater than 18 doses prior to their CEA.

We will include patients who are either statin naïve, assuming no history of adverse experience with a statin, or on one of three types of statins: simvastatin, atorvastatin, or rosuvastatin. Patients will be enrolled, and based on their preexisting statin regimen, they will be grouped into one of three arms prior to CEA: ARM 1) Patients on a pre-existing maximal daily dose statin regimen will be observed, ARM 2) Patients on a pre-existing statin regimen at sub-maximal doses will be randomized to maintain their current dose plus placebo or current dose plus the necessary milligrams to reach maximal daily dose, and ARM 3) Patients who are on no preexisting statin regimen, statin naïve in the last 30 days, will be randomized to atorvastatin

10mg or atorvastatin 80mg for no fewer than 2 and no greater than 18 daily doses before their CEA (Figure 6).

As per the simvastatin drug insert, patients taking amlodipine (Norvasc) should not exceed 20 mg of simvastatin; therefore, we will only potentially increase any patient who is also on amlodipine to daily doses of 20 mg and not 40 mg. Consequently:

- *If subject is on 40 mg simvastatin without amlodipine – they will be in ARM 1 (observational)
- *If subject is on 40 mg simvastatin + amlodipine – they will be in ARM 1 (observational)

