4.2 Exclusion Criteria

- 1) Patient has underlying disease other than atherosclerosis (i.e. autoimmune disease, known active malignancy).

- 2) Patient has documented dementia or screens out based on abnormal Baseline MoCA (≤ 25) and AD8 (≥ 2).
- 3) Patient's life expectancy is < 12 months.
- 4) Patient has advanced renal failure (serum creatinine > 2.5 mg/dL)
- 5) Patient has evidence of severe congestive heart failure or has history of end-stage cardiovascular disease (e.g. CHF NYHA Class III or IV or unstable angina).
- 6) Patient has history of intolerance or allergic reaction to any statins (myotoxicity, hepatic dysfunction, rash, etc.) – unless they would be in the Observational Arm (Arm 1) and therefore will not be receiving any study drug.
- 7) Patient has received an investigational drug within 30 days.
- 8) Patient is pregnant or lactating.
- 9) Except those eligible for the Observational Arm who do not receive any study statin, patient who is currently taking any of the following which have been shown to interact with atorvastatin and/or simvastatin and/or rosuvastatin (as per current drug package inserts):
 - *Cyclosporine;
 - *HIV Protease Inhibitors/Antivirals (e.g. roatanavir or plus roatanavir, tipranavir, lopinavir, boceprevir, saquinavir, darunavir, fosamprenavir, nelfinavir, efavirenz/tenofobir, atazanavir, simeprevir);
 - *Hep C Protease Inhibitor/Antivirals (e.g. telaprevir);
 - *Antibiotics (i.e. cobicistat-containing products like Tybost, rifampin/rifampicin, clarithromycin, telithromycin, erythromycin);
 - *Anti-fungals (i.e. itraconazole, ketoconazole, posaconazole, voriconazole, fluconazole); *Gemfibrozil; Other Fenofibrates (e.g. Tricor, fibric acid);
 - *Niacin > 1 g/day or statins in combination with niacin (e.g. Vytorin, Simcor);
 - *Colchicine;
 - *Danazol;
 - *Calcium Channel Blockers: Diltiazem, Varapamil;
 - * Dronedarone;
 - *Amiodarone;
 - *Digoxin;
 - *Ranolazine;
 - *Nefazodone;
 - *Warfarin/Coumadin;
 - *Lomitapide;
 - *Grapefruit juice (subject must be willing to avoid grapefruit juice).

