9.2.1 Treatment Assignment Procedures

The randomization design will be stratified by center, previous use of statin and in random blocks of 4 and 6. The randomization process will be supported by the Statistical Analysis Center (SAC) at the Mailman School of Public Health at Columbia University. SAC will provide a central secure web-based randomization data system. All trials supported by the SAC employ central randomization that takes place in real-time. In other words, the patient's treatment assignment is made at the moment of randomization, based on probabilities calculated according to the randomization scheme, and communicated to the recruiting site via a central source (i.e. a secure web site).

- Patients on maximum dose of one of the three statins will be maintained on that dose (ARM 1). This arm will contain 225 participants.

- Those patients on submaximal doses of the 3 study statins will be randomized to their current dose plus placebo or their current dose plus the additional milligrams necessary to bring to raise them to the maximal daily dose of simvastatin (40 mg) or atorvastatin (80 mg) or rosuvastatin (20 mg) depending on which statin they are already on, (ARM 2). There will be 337 participants maintained at their current dose and 338 raised to the maximum dose of their statins.
- If patients are statin naïve, then they will be randomized to either atorvastatin 10 mg or 80 mg daily (ARM 3). ARM 3 will have 50 participants in each arm.

The randomization will be performed automatically by the web-based data system. No one will have access to unblinded treatment information on a regular basis other than the packaging pharmacy. All handling of study medication will take place using blinded bottle codes. It is not expected that serious adverse events will require revelation of treatment assignment, but the study web site will provide for online unblinding in emergencies. Revelation of treatment assignment will be available only to authorized users, who will be required to provide a clinical justification for unblinding. Each case of unblinding will be addressed by study personnel to ensure access to unblinded treatment assignment information is limited, and that such incidents are limited to circumstances where it is necessary for the health of the patient.

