10.3.2 Protocol Deviations

Any study protocol deviation/violation must be documented in the subject binder, submitted to site's IRB (as per their rules and regulations) and the CCC team for review (see Appendix V). Some of the protocol deviations will also provide a metric for identifying sites that may need further training.

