***DEVIATION CATEGORIES:**

- A. Safety
- B. Informed Consent
- C. Eligibility
- D. Protocol implementation
- E. Other, specify in log

****DEVIATION CODES:** Numbers listed by the sample protocol deviations

Safety (Category A)

- 1. Not reporting an SAE within 24 hours
- 2. Laboratory tests not done
- 3. AE/SAE is not reported to IRB
- 4. Other, specify in log

Informed Consent (Category B)

- 5. Failure to obtain informed consent

- 6. Consent form used was not current IRB-approved version
- 7. Consent form does not include updates or information required by IRB
- 8. Consent form missing
- 9. Consent form not signed and dated by participant
- 10. Consent form does not contain all required signatures
- 11. Other, specify in log

Eligibility (Category C)

- 12. Participant did not meet eligibility criterion
- 13. Randomization of an ineligible participant
- 14. Participant randomized prior to completing Baseline Assessment, etc.
- 15. Randomization and/or treatment of participant prior to IRB approval of protocol
- 16. Other, specify in log

Protocol implementation (Category D)

- 17. Failure to keep IRB approval up to date

- | | |
|---|---------------------------|
| 18. Participant receives wrong treatment | 22. Missed assessment |
| 19. Participant seen outside visit window | 23. Missed visit |
| 20. Use of unallowable concomitant treatments | 24. Other, specify in log |
| 21. Prescribed dosing outside protocol guidelines | |

- **Appendix V: Primary Medical Doctor Letter:**

**Statin Neuroprotection and Carotid Endarterectomy:
Safety, Feasibility and Outcomes" (STANCE)**
Columbia University Medical Center
Department of Neurological Surgery
[name]
[name]

[date]

RE: [name]

Dear Doctor [name of PMD]:

DOB: [DOB]

This letter is to inform you that your patient has elected to take part in a research study entitled, Statin Neuroprotection and Carotid Endarterectomy: Safety, Feasibility and Outcomes" (STANCE). The study is sponsored by the National Institutes of Aging (NCT02850081) and is being conducted at multiple sites in the US including Columbia University Medical Center.

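### Section 5.3.3 asks all subjects to avoid the Exclusion 9 drugs without repeating the Arm 1 exception, and Section 7.3 drops the Exclusion 6 exception in the same way

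*Combined protocol and SAP*

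**What the plan says.** **Eligibility (Section 4.2).** Exclusion 9 bars patients taking any of a list of interacting drugs, but opens with an exception: "Except those eligible for the Observational Arm who do not receive any study statin". Exclusion 6, on past intolerance or allergy to statins, carries a similar exception for patients who would be in Arm 1.

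**Conduct (Section 5.3.3).** The third bullet introduces the same list: "Subjects will be screened for and asked not to concurrently take the following medications during the study dosing period prior to CEA". No arm is named and no exception is given.

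**What Arm 1 does (Section 5.1).** Arm 1 subjects "will continue to take their daily statin during the dosing period prior to CEA". Of study drug, the section says: "No additional drug will be dispensed to this group".

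**Allowed therapy (Section 5.3.1).** Standard-of-care drugs, including those for cardiovascular risk factors and other comorbid conditions, are permitted provided the Section 4.2 criteria are observed. Arm 1 is not mentioned.

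**Deviations.** The log in Appendix IV has code 20, "Use of unallowable concomitant treatments". Under Section 10.3.2 deviations go to the coordinating centre, and: "Some of the protocol deviations will also provide a metric for identifying sites that may need further training".

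**Side effects (Section 7.3).** Patients with side effects at their present statin dose or a higher one are not to be enrolled. Again there is no exception for Arm 1.

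**The concern.** The protocol grants Arm 1 an exception in one place and then states the matching rule elsewhere without it. Take a patient on a maximal statin dose plus long-term warfarin. Exclusion 9 admits this patient to Arm 1. Section 5.3.3 then asks the patient not to take warfarin until surgery. The list also contains amiodarone, digoxin and cyclosporine. The reason that Exclusion 9 gives for its exception, that no study statin is received, applies equally in the dosing period, so the request has no study-drug reason behind it.

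Two things are at stake. One is an avoidable request to change established medication shortly before carotid endarterectomy. The other is inconsistent deviation logging: a site that reads Section 5.3.3 literally could record code 20 for a patient whom another site would regard as fully compliant.

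Section 7.3 raises a separate and narrower problem of the same kind. It would turn away an Arm 1 candidate with past statin side effects whom Exclusion 6 would admit.

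**Working it through.** This is a comparison of texts; the plan gives no figure to reproduce.

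**1. Are the lists the same?** Exclusion 9 has 18 starred entries, from cyclosporine to grapefruit juice. Section 5.3.3 has 18. All 18 appear in both: 17 drugs or drug classes, plus grapefruit juice.

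**2. Is the exception carried over?**

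| Place | Rule | Arm 1 exception |
|---|---|---|
| 4.2, Exclusion 9 | Listed drugs bar enrolment | Yes |
| 5.3.3, third bullet | Listed drugs to be avoided in the dosing period | No |
| 4.2, Exclusion 6 | Statin intolerance bars enrolment | Yes |
| 7.3 | Side effects at current or higher doses bar enrolment | No |

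**3. Does the wording of Section 5.3.3 reach Arm 1?** Section 5.1 calls Arm 1 participants subjects and gives them a dosing period before surgery, which are the two terms that Section 5.3.3 uses. The first bullet of Section 5.3.3, against switching statins in the dosing period, also makes sense for Arm 1, which is meant to stay on its current statin. A narrower reading exists: Sections 3 and 5.2 tie the dosing period to study capsules and bottles, which Arm 1 does not receive. The text does not say which reading applies.

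**4. Does another section resolve it?** Section 5.3.1 refers back to Section 4.2, and so by implication to its exceptions. It neither names Arm 1 nor limits Section 5.3.3. For the warfarin patient, Section 5.3.1 points to allowed and Section 5.3.3 to prohibited.

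**5. How many patients?** Section 9.2.1 gives the planned size of Arm 1: "This arm will contain 225 participants". The ceiling for Section 5.3.3 is therefore 225 of 1,000, or 225 / 1,000 = 22.5%. The documents give no rate of use of the listed drugs in Arm 1, so the number lies somewhere from 0 to 225. Randomised patients number 675 + 100 = 775, and the missing exception concerns none of them. The Section 7.3 point concerns candidates who would not be enrolled, and the documents give no count of those.

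**The case against.** The best reply is that the two rules do different jobs. Exclusion 9 decides who may enrol; Section 5.3.3 governs conduct afterwards and only makes a request. A patient can be eligible under one and receive a request under the other. Section 5.3.1 can also be read as positively allowing the drug, since a patient exempt under Exclusion 9 observes Section 4.2. On that view this is a qualifier left unrepeated, and code 20 would not apply because the drug is not unallowable.

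Much of this stands. It shows the likely intent and keeps the point small. It does not remove the point, because a site must still choose between a heading that says prohibited and an allowance that does not mention Arm 1.

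Four stronger readings are tempting and are not supported:

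- **That Arm 1 patients would be taken off needed drugs.** No passage orders washout or withdrawal, and Section 8 does not list use of these drugs as a reason to stop study treatment.
- **That sites would be retrained because of this.** Section 10.3.2 says only that some deviations serve as a metric; nothing places code 20 among them.
- **That the amlodipine rule in Section 3 shows how listed drugs are handled in Arm 1.** Amlodipine is not on the list, whose calcium channel blockers are diltiazem and verapamil.
- **That the comparison of Arm 1 with the supplemented half of Arm 2 is distorted.** No analysis exclusion is tied to Section 5.3.3, all analyses follow intention to treat, and the number of patients concerned is unknown.

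A further objection also stands: exempting Arm 1 altogether would remove the request not to start a listed drug, such as clarithromycin, while on a maximal statin dose. Exclusion 9 speaks of drugs that the patient is already taking. The exception should be limited to those.

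On Section 7.3, the opening of Section 4 makes the criteria there the test for enrolment, so Exclusion 6 should prevail. That makes the conflict easy to settle, but Section 7.3 is still worded as a bar.

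**Conclusion.** The point holds as a minor, operational inconsistency. Read literally, Section 5.3.3 covers eligible Arm 1 patients on an established listed drug, and no other section settles that it does not. Section 7.3 omits the Exclusion 6 exception independently; it conflicts only for Arm 1 candidates with such side effects and adds no weight to the main point.

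The conclusion depends on a site taking subjects and dosing period in the sense of Section 5.1. A site that ties the dosing period to study drug would see no conflict, so the consequence is conditional.

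The effect on patients cannot be sized beyond the Arm 1 ceiling. The randomised comparisons within Arms 2 and 3, alpha and power are unaffected: no patient leaves an analysis set, and no planned group size changes because of Section 5.3.3.

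**What to change.** In the third bullet of Section 5.3.3, add: *except Arm 1 subjects already taking a listed drug at enrolment, whose medication is left to the treating physician and is not a deviation*. Keep the request not to start a listed drug newly for all arms.

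In Section 7.3, add to the sentence on side effects: *except Arm 1 candidates, per Exclusion 6*.

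The cost is one phrase in each section and a short note to sites so that code 20 is logged the same way everywhere. No new data, visits or patients are needed.
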